# 13.4.3.2 Secondary and Exploratory Analyses

Secondary and exploratory analyses will include analysis of the combined score by subject type, OMERACT-OARSI responders, KOOS subscale (including AUCs), and SS.

All continuous secondary and exploratory efficacy endpoints will be summarized using descriptive statistics by week/visit, as appropriate, and analyzed using an MMRM analysis or by analysis of covariance, as appropriate. Categorical endpoints will use Pearson's chi-square or Fisher's exact test, as appropriate. *P* values from exploratory endpoints will be considered nominal and no adjustments for multiplicity will be made.

# 13.4.4 Safety and Tolerability Analyses

Safety analyses will be conducted using data from the safety population (as defined in Section 13.3). Safety variables include injection site assessments (erythema and edema), assessment of procedure pain, AEs, physical examination findings, vital sign measurements, 12-lead ECG findings, clinical laboratory test results, and sensory testing. No formal inferential analyses will be conducted for safety variables unless otherwise noted.

#### 13.4.4.1 Adverse Events

All AEs will be coded using the Medical Dictionary for Regulatory Activities (MedDRA), Version 16.0 or higher.

Treatment-emergent AEs are defined as:

• AEs with onset at the time of or following the start of treatment with CNTX-4975-05 through the Week 8/ET Visit

The number and percentage of subjects with AEs will be displayed for each injection procedure by system organ class and preferred term. Summaries of AEs by severity and relationship to CNTX-4975-05 will also be provided. Serious AEs and AEs resulting in discontinuation of CNTX-4975-05 will be summarized separately in a similar manner. Subject listings of AEs, SAEs and AEs causing discontinuation of CNTX-4975-05 will be produced.

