- n. The injection site will be examined and assessed for erythema and edema by site personnel (using a categorical 4-point scale of none, mild, moderate, or severe [0-3]) on Study Day 1 (Treatment) before injection, after the injection at 1 and 2 hours post-dose, and at the Week 4 Visit. For bilateral knee injections, injection site examinations will be performed before and after each injection. Significant bruising or other clinically significant injection site reactions will be recorded as AEs.
- o. Procedure pain will be assessed by asking subjects to rate their index knee pain (1) at rest prior to pre-medication; (2) prior to IA lidocaine (without epinephrine); (3) at rest 10 minutes (± 2 minutes) after IA lidocaine (without epinephrine); (4) at 30 minutes (± 5 minutes) after IA injection of CNTX-4975-05; and (5) at rest at the 1-hour and 2-hour time points after IA injection of CNTX-4975-05 (± 10 minutes).
- p. Immediately prior to leaving the clinic, the subject will be asked how satisfied they were with the treatment procedure at that visit, using a 7-point Likert Scale where 1=completely dissatisfied and 7=completely satisfied. Subjects with a PJR/TJR will also compare their satisfaction with PJR/TJR versus the CNTX-4975-05 treatment.
- q. Subjects will be asked whether they would undergo the study treatment again.
- r. The investigator will rate their satisfaction with each subject's study treatment (at V2 and V4 if applicable) and the treatment procedure (at V7).
- s. The investigator will judge the likelihood of the need for joint replacement surgery, based on KOOS subscales and subject satisfaction outcomes. The subject will judge the likelihood of the desire for joint replacement surgery, based on their personal response to treatment with CNTX-4975-05.
- t. Collection of AEs will begin from the time of signing the informed consent form through the Week 8/ET Visit. On Day 1, the AE assessment must be performed pre-dose. Treatment-emergent AEs will be collected from the time of the injection of CNTX-4975-05 through the Week 8/ET Visit. Potentially

13-Jun-2019 Amendment 2 Version: 3.0

AD-MW-08.04 15-Apr-2016 Page 17 of 89

- related AEs that are ongoing at the Week 8/ET Visit will be followed until they are stable, resolved, no longer clinically significant (in the opinion of the investigator), or until 4 weeks after the study is completed.

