### 9.3.3 Injection of CNTX-4975-05

It is recommended that the CNTX-4975-05 injection be administered using ultrasound-guided needle placement, but is not required. If imaging-guided injection is not used, then confirmation of location of the needle within the index knee joint must be verified by aspirating joint fluid. If no joint fluid is aspirated, CNTX-4975-05 should not be injected. If there is a substantial effusion within the knee joint, the effusion should be aspirated, when possible, such that the estimated remaining joint fluid in the knee is approximately 5-10 mL. Record the amount of joint fluid aspirated.

Subjects should not take a hot bath or shower, or expose the injected knee(s) to external heat, within 12 hours after the injection.

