### 11.1.5 Treatment-Emergent Adverse Events

An AE is defined as treatment emergent if the first onset or worsening is after the first administration of IP.

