### 11.2.3.5 Adverse Event Relationship to Investigational Product

The investigator must make an assessment of each AE's relationship to the IP. The categories for classifying the investigator's opinion of the relationship are listed below.

Not related	An AE with sufficient evidence to accept that there is no causal relationship to IP administration (e.g., no temporal relationship to drug administration, because the drug was administered after onset of event; investigation shows that the drug was not administered; another cause was proven).
Unlikely related	An AE, including laboratory test abnormality, with a temporal relationship to IP administration that makes a causal relationship improbable, and in which other drugs, events or underlying disease provide plausible explanations.
Possibly related	An AE with a reasonable time sequence to administration of the IP, but which could also be explained by concurrent disease or other drugs or events. Information on drug withdrawal may be lacking or unclear.

\*Only select fatal as an outcome when the AE results in death. If more than one AE is possibly related to the subject's death, the outcome of death should be indicated for each such AE. Although "fatal" is usually an event outcome, events such as sudden death or unexplained death should be reported as SAEs.

Related

An AE occurring in a plausible time relationship to IP administration and which cannot be explained by a concurrent disease or other drugs or events. The response to withdrawal of the drug (dechallenge) is clinically reasonable.

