#### 11.2.4 Documentation

All AEs occurring within the period of observation for the study must be documented in the eCRF with the following information, where appropriate. (The period of observation for the study is described in Section 11.2.)

- AE name or term
- When the AE first occurred (start date and time)
- When the AE stopped (stop date and time or an indication of "ongoing")
- Severity of the AE
- Seriousness (hospitalization, death, etc.)
- Actions taken
- Outcome
- Investigator opinion regarding the AE relationship to the IP(s)

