#### 13.3 Analysis Populations

The following analysis populations are planned for this study: The following analysis populations are planned for this study:

- Safety: all subjects who receive any amount of planned CNTX-4975-05.
- Intent-to-Treat (ITT): all enrolled subjects.

Membership in the analysis populations will be determined prior to database lock.

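### Treatment-emergent status and the safety population are tied to the drug injection, so a treatment-emergent comparison would start its clock at a different point in each regimen

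*Combined protocol and SAP*

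**What the plan says.** Three places tie treatment-emergent status to the study drug.

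- Section 13.4.4.1: "AEs with onset at the time of or following the start of treatment with CNTX-4975-05 through the Week 8/ET Visit".
- Section 11.1.5: "An AE is defined as treatment emergent if the first onset or worsening is after the first administration of IP".
- Footnote t to Table 2-1: "Treatment-emergent AEs will be collected from the time of the injection of CNTX-4975-05 through the Week 8/ET Visit".

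The analysis set follows the same rule. Section 13.3 has "Safety: all subjects who receive any amount of planned CNTX-4975-05", and Section 13.4.4 runs the safety analyses on that set.

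Causality is also framed around the drug. Section 11.2.3.5 states "The investigator must make an assessment of each AE's relationship to the IP", and one of its examples of an unrelated event is "no temporal relationship to drug administration, because the drug was administered after onset of event". The documentation list in Section 11.2.4 likewise asks only about the IP.

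Two provisions pull the other way. Section 11.2 collects adverse events from consent onwards. The by-procedure table in Section 13.4.4.1 is worded as a table of AEs, without the qualifier treatment-emergent, although it comes directly after that definition.

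**The concern.** The primary objective (Section 6.1) is to find the best way of administering the drug. Each site is randomised to one of five regimens (Section 9.3.2), which share the drug and differ in cooling device and duration, lidocaine strength, and one needle or two. Much of what distinguishes them happens before the drug goes in: all of the pre-cooling, the full lidocaine injection and the wait after it.

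A clock that starts at the drug suits the drug safety objective in Section 6.4. For comparing regimens, it starts after a pre-drug period that differs between the arms in length and content. If the by-procedure table uses the treatment-emergent definition, the arms are counted from different points in the procedure. A difference between them could then reflect the counting rule rather than the regimen.

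In addition, a subject who starts cooling or lidocaine and never receives drug is outside the safety population. If a reaction to one of those steps was the reason for stopping, which the documents do not discuss, the event would be highly informative about the regimen and would still be missing from its safety tables.

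**Working it through.** The plan states no figure on this point, so there is nothing to reproduce. The inputs are the first-knee step times in Section 9.3.2.

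**Step 1: where the clock starts.** Minutes from start of cooling to drug = pre-cooling + interval from lidocaine to drug. Injection times and the ±5-minute allowance for moving the subject are ignored.

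| Group | Pre-cool (min) | Lidocaine to drug (min) | Start of cooling to drug (min) |
|---|---|---|---|
| 1 (Breg control) | 15 | 30 | 15 + 30 = 45 |
| 2 | 40 | 10 | 40 + 10 = 50 |
| 3 | 30 | 5 | 30 + 5 = 35 |
| 4 | 45 | 3 | 45 + 3 = 48 |
| 5 | 45 | 3 | 45 + 3 = 48 |

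**Step 2: the same event in each arm.** A reaction starting *t* minutes after lidocaine is treatment-emergent only if *t* is at least the lidocaine-to-drug interval.

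- *t* = 4: Groups 4 and 5 only.
- *t* = 7: Groups 3, 4 and 5.
- *t* = 15 or 25: Groups 2 to 5, but not the control.

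For events timed from the start of cooling, the order changes. An event at 40 minutes counts only in Group 3 (40 ≥ 35, but below 45, 48 and 50).

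**Step 3: illustration of size.** The documents give no reaction rate or onset time. Assume equal true rates of lidocaine reaction in all arms, exponential onset after lidocaine, and drug given on schedule. The share counted as treatment-emergent is then 0.5^(lidocaine-to-drug interval / median onset). At a 10-minute median, for example, Group 1 gives 0.5^(30/10) = 0.125 and Group 4 gives 0.5^(3/10) = 0.812.

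| Assumed median onset (min) | Group 1 | Group 2 | Group 3 | Groups 4 and 5 |
|---|---|---|---|---|
| 2 | 0% | 3% | 18% | 35% |
| 5 | 2% | 25% | 50% | 66% |
| 10 | 13% | 50% | 71% | 81% |
| 30 | 50% | 79% | 89% | 93% |

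The control is lowest in every row.

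**Step 4: whether other safety data fill the gap.** Only in part. Procedure pain is not recorded as an AE (Section 13.1.4), and Section 13.4.4.8 does not say it will be summarised by regimen. The reading 10 minutes after lidocaine nominally falls before drug in Group 1, at about the time of drug in Group 2, and after drug in Groups 3 to 5. Erythema and edema are assessed before injection, at 1 and 2 hours after it, and at Week 4 (Section 10.3.3.2.4).

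**The case against.** A reader might infer that the harms of cooling, lidocaine and needle all drop out of the regimen safety comparison. The documents do not support that. Events are collected from consent with start times, and footnote t requires a pre-dose AE assessment on Day 1. Read literally, the by-procedure table would include pre-drug events in subjects who go on to injection. Post-dose cooling follows the drug in every regimen, so its harms are treatment-emergent. So are later-onset harms of any step, and all second-knee steps in bilaterally treated subjects. What stands is that Section 13.4.4.1 defines one set of events and then does not say which set it tabulates.

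A reader might also infer that a regimen could be declared acceptable because its harms were missed. It could not. Acceptability in Section 13.4.3.1 rests only on the composite of pain and two satisfaction scores against the 0.7 limit. Adverse events play no part, and the safety summaries are descriptive.

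Section 9.3.3 might be taken to show that subjects will be given lidocaine and then no drug: "If no joint fluid is aspirated, CNTX-4975-05 should not be injected". That route is narrower than it looks. The rule applies only when imaging is not used, and the Synopsis asks for joint fluid in the needle hub before lidocaine as well as before drug, so a failed check would normally stop both. A failure at the second needle remains possible in Groups 1 to 3, and a subject may stop after cooling alone. The documents give no frequency. Such subjects might show in the disposition tables (Section 13.4.1.1) but not in the safety tables.

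On causality, it would be too strong to say that no harm can be attributed to the procedure. The categories in Section 11.2.3.5 allow for another cause. What is absent from the documented items is a structured question about the procedure. The eCRF is not available, so its absence there cannot be confirmed.

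Finally, Section 13.4 defers detail to an analysis plan to be written before database lock, which is not among the documents reviewed. That plan could settle the matter, but as written the matter is open.

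**Conclusion.** The point holds in a limited form. Treatment-emergent status and safety-population membership are anchored to a drug that all arms share, while the regimens differ in the steps around it. Any treatment-emergent comparison would start nominally 30, 10, 5, 3 and 3 minutes after lidocaine in Groups 1 to 5, and would count an early first-knee lidocaine reaction least often in the control. Over assumed median onsets of 2 to 30 minutes, the share counted runs from 0 to 50% in the control and from 35 to 93% in Groups 4 and 5. These shares rest on the exponential model and on equal true rates. They show the direction and possible extent of the distortion and do not predict numbers of events.

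The distortion is conditional on the by-procedure table being limited to treatment-emergent events, which the plan neither states nor rules out. The exclusion of subjects who start a regimen step but receive no drug does not depend on that reading; how many there would be is unknown.

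**What to change.** For the adverse-event tables by regimen:

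1. Count events from the first regimen step on the first treatment day (pre-medication or start of pre-cooling), and state this in Section 13.4.4.1.
2. Base these tables on all subjects who start any step of the assigned regimen, and define that set in Section 13.3.
3. Keep the existing treatment-emergent tables and the drug-exposed safety population alongside, for the drug safety objective.
4. Optionally, record relationship to procedure (cooling, lidocaine, needle) next to relationship to the IP in Sections 11.2.3.5 and 11.2.4, and tabulate it by regimen.

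The cost is small. Section 11.2.4 already asks for event start date and time, so items 1 to 3 need wording and one additional set of tables. Item 4 needs one eCRF field if none exists. Adverse-event counts in the regimen tables may be slightly higher than in the drug-based tables, and the report should explain why the two differ.

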#### 13.4.4.2 Clinical Laboratory Evaluations

Descriptive summaries (mean, SD, median, minimum, and maximum) of actual (absolute) values and changes from Baseline values will be presented for clinical laboratory values at each time point.

The number of subjects with clinical laboratory values categorized as below, within, or above normal ranges, will be tabulated showing change from Baseline (shift tables) for each clinical laboratory analyte by study visit. Pre- and post-treatment values will also be presented with analysis summary of mean changes from Baseline.

Laboratory values that are outside the normal range will also be flagged in the data listings, along with corresponding normal ranges. Any out-of-range values that are identified by the investigator as being clinically significant will be reported as AEs.

# **13.4.4.3 Vital Signs**

Descriptive summaries (mean, SD, median, minimum, and maximum) of actual values and changes from Baseline will be calculated for systolic blood pressure, diastolic blood pressure, HR, and RR.

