## **REASONS FOR AMENDMENT**

- 1. The addition of acute allergic/anaphylactic/anaphylactoid reaction as an adverse event of special interest, with new precautions, clinical criteria, assessments, and treatment protocols.
- 2. The addition of vital sign assessments 15 and 30 minutes after injection of study drug.
- 3. The addition of a 30-minute post-injection observation period to ensure that subjects do not have a hypersensitivity reaction/anaphylaxis.
- 4. The addition of crash carts and ACLS-certified personnel to the requirements at each study site.

[figure not shown]
AD-MW-08.04 15-Apr-2016 Page 24 of 89

[figure not shown]
Amendment 2 Version: 3.0

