### 5. Single Needle Injection Gel Pack Cooling Group-1% IA Lidocaine

- a. Gel pack cooling applied for 45 minutes to the knee using the gel pack over a stockinette or light-weight pants. This may be outside of the exam room, but at the investigator's discretion, may be done in the exam room. If done outside the exam room, subject may be moved to the exam room ± 5 minutes of the 40-minute cooling (with gel pack remaining on the knee).
- b. Inject IA the full 15 mL 1% lidocaine (without epinephrine) into the knee joint using appropriate aseptic techniques.
- c. After the 1% lidocaine IA injection, CNTX-4975-05 IA injection, using the same needle, will be injected into the knee joint using appropriate aseptic techniques after 3 minutes of the 1% lidocaine (without epinephrine).
- d. Gel pack cooling may be reapplied for up to 90 minutes, as needed, after CNTX-4975-05 injection, depending on the subject's comfort. The subject may remain in the exam room, or be moved to a more comfortable area with the gel pack. The gel pack may be discontinued after IA CNTX-4975-05 injection if the subject has a pain level that is acceptable for the subject and investigator (0-4 scale: none, mild, moderate, moderately severe and severe).

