#### 10.1 Study Visits

### 10.1.1 Screening Visit, Day -14 to Day 1, Visit 1

The subject must be screened within 14 days before enrollment into the study. The following procedures will be performed at screening.

- Written informed consent
- Confirmation of knee OA K-L grade (1 to 4) of the knee, based on radiographs
- Confirmation of diagnosis of knee OA, based on ACR diagnostic criteria
- Inclusion/exclusion criteria
- Height and weight (BMI)
- History of cancer
- Knee pain with walking (during last 24 hours, assessed in the clinic using NPRS of 0-10)
- Demographics
- Medical history, including current OA medications (prescription and non-prescription medications) and treatment history (including noninvasive or previous invasive treatments)
- HADS
- FSS
- Knee circumference
- Complete physical examination
- ECG
- Clinical laboratory testing (fasting)
- Urine drug screen
- Urine pregnancy test
- Vital signs
- Issue paper diary to the subject with instructions on use and recording of background analgesic and rescue medication for index knee (or bilateral knee for subjects being treated for both knees)

### 10.1.2 Treatment, Day 1, Visit 2

As 2 cases of severe allergic reactions have occurred in the entire CNTX-4975 program, a crash cart and personnel certified in advanced cardiac life support (ACLS) should be immediately available. See section 11.2.1 for details.

The following procedures will be performed on Day 1.

- Knee pain with walking (during last 24 hours, assessed in the clinic using NPRS of 0-10)
- Partial physical examination
- ECG
- Urine drug screen
- Urine pregnancy test
- Vital signs (before and after injection of CNTX-4975-05). All subjects must be monitored for at least 30 minutes (or longer, as required by the protocol) after study drug injection to ensure that they do not have a hypersensitivity reaction/anaphylaxis. Vital signs (VS) are to be done standing and sitting within approximately 5 minutes before the injection of IP, and sitting-only vital signs within approximately 5, 15, and 30 minutes after the injection of IP.
- Injection site assessment (erythema, edema) before injection and 1 and 2 hours after the injection
- Review paper diary
- Sensory testing
- Subject assessment of procedure pain (using 0-4 scale)
  - o at rest prior to pre-medication;
  - o prior to IA lidocaine (without epinephrine);
  - o at rest 10 minutes (±2 minutes) after IA lidocaine (without epinephrine);

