#### 10.3.3.2 Clinical Examinations

#### **10.3.3.2.1 Vital Signs**

Vital signs measurements will be conducted according to the schedule of events, Section 2 and will include systolic and diastolic blood pressure, heart rate (HR) and respiratory rate (RR), and will be measured with the subject standing and also after the subject has been in a sitting position for 5 minutes. Temperature will also be measured at all office visits.

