## **Anaphylactoid reaction**

These reactions produce the same clinical signs and symptoms anaphylactic reactions, but are not IgE mediated, but instead occur through a direct non-immune-mediated release of mediators from basophils and/or mast cells or can manifest from direct complement activation.

All subjects must be monitored for at least 30 minutes (or longer, as required by the protocol) after study drug injection to ensure that they do not have a hypersensitivity reaction/anaphylaxis. Vital signs (VS) are to be done pre-injection and 5 minutes after the injection, standing and sitting, and then vital signs must now be taken at 15 and 30 minutes (sitting only) after injection of study drug

Any subject that meets the criteria for anaphylaxis or anaphylactoid reactions, as described in the paper by Sampson et al. (2006) (see Appendix C) following the first/prior injection is prohibited from being re-treated with study drug.

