### Clinical Criteria for Diagnosing Anaphylaxis

Anaphylaxis is highly likely when any **one of the following 3 criteria** are fulfilled:

- 1. Acute onset of an illness (minutes to several hours) with involvement of the skin, mucosal tissue, or both (eg, generalized hives, pruritus or flushing, swollen lips-tongue-uvula), AND AT LEAST ONE OF THE FOLLOWING:
  - a. Respiratory compromise (eg, dyspnea, wheeze-bronchospasm, stridor, reduced PEF, hypoxemia)
  - b. Reduced BP or associated symptoms of end-organ dysfunction (eg, hypotonia [collapse], syncope, incontinence)
- 2. Two or more of the following that occur rapidly after exposure to a likely allergen for that patient (minutes to several hours):
  - a. Involvement of the skin-mucosal tissue (eg, generalized hives, itch-flush, swollen lips-tongueuvula)
  - b. Respiratory compromise (eg., dyspnea, wheeze-bronchospasm, stridor, reduced PEF, hypoxemia)
  - c. Reduced BP or associated symptoms (eg, hypotonia [collapse], syncope, incontinence)
  - d. Persistent gastrointestinal symptoms (eg, crampy abdominal pain, vomiting)
- 3. Reduced BP after exposure to known allergen for that patient (minutes to several hours):
  - a. Infants and children: low systolic BP (age specific) or greater than 30% decrease in systolic BP\*
  - b. Adults: systolic BP of less than 90 mm Hg or greater than 30% decrease from that person's baseline

Source: Sampson et al. (2006)

Abbreviations: PEF, Peak expiratory flow; BP, blood pressure.

\* Low systolic blood pressure for children is defined as less than 70 mmHg from 1 month to 1 year, less than (70 mmHg +  $[2 \times age]$ ) from 1 to 10 years, and less than 90 mmHg from 11 to 17 years.

Page 63 of 89

Amendment 2 Version: 3.0

13-Jun-2019

In the event of an anaphylactic reaction or anaphylactoid event, institute treatment immediately, as outlined in Appendix C. Note also that a serum tryptase blood level must be obtained using the Vacutainer tube provided.

All anaphylactic and anaphylactoid events (e.g. rash, dyspnea, gastrointestinal symptoms) must be recorded with the time that the events occurred and resolved, and treatments (e.g. epinephrine) should be recorded with their time of administration.

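### Vital signs are summarised only by means and extremes, so post-injection blood-pressure falls that pass the protocol's own cut-off but are not reported as AEs are not systematically counted by regimen

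*Combined protocol and SAP*

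**What the plan says.** **Analysis.** Section 13.4.4.3 covers systolic and diastolic pressure, heart rate and respiratory rate: "Descriptive summaries (mean, SD, median, minimum, and maximum) of actual values and changes from Baseline will be calculated". It names no threshold, time point, posture or regimen, and it does not define Baseline.

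**Why the readings were added.** The Reasons for Amendment list "The addition of vital sign assessments 15 and 30 minutes after injection of study drug" and, next to it, "The addition of a 30-minute post-injection observation period to ensure that subjects do not have a hypersensitivity reaction/anaphylaxis".

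**Cut-off.** The only numerical blood-pressure limit for adults is in the anaphylaxis criteria of Section 11.2.1: "Adults: systolic BP of less than 90 mm Hg or greater than 30% decrease from that person's baseline".

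**Posture at 5 minutes.** Section 11.2.1 says "Vital signs (VS) are to be done pre-injection and 5 minutes after the injection, standing and sitting". Section 10.1.2 says "sitting-only vital signs within approximately 5, 15, and 30 minutes after the injection of IP"; Section 10.1.4 and the vital-signs footnote to Table 2-1 agree with it. The general text in Section 10.3.3.2.1 asks for a standing reading and one "also after the subject has been in a sitting position for 5 minutes".

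**Pre-dose timing.** Table 2-1 and Sections 10.1.2 and 10.1.4 ask for standing and sitting readings within about 5 minutes before study drug. In Group 5, study drug goes through the same needle "after 3 minutes of the 1% lidocaine" (Section 9.3.2). Group 4 has the same interval with 2% lidocaine.

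**The concern.** The amendment responds to a rare, individual event, and the added readings are analysed with statistics that describe a group. Elsewhere the same plan counts subjects: laboratory values get shift tables (Section 13.4.4.2), and QT/QTc changes above 30 and 60 ms get numbers and percentages (Section 13.4.4.4). Vital signs, the measurement that was expanded, get no such count.

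At stake is whether the report can say how many subjects in each regimen had a marked fall, whether or not an investigator called it an event. The sample size is justified by safety requirements for regulatory review (Section 13.2). There is no data safety monitoring board (Section 12), and interim output is to match the final analyses (Section 13.4.5), so an interim safety review would have the same gap.

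The posture and window passages are a separate matter. Sites that follow different passages will collect different sets of readings, and the reading available as a pre-dose value may sit differently relative to lidocaine across regimens.

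**Working it through.** The plan states no figure on this point, so there is none to reproduce.

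**1. What the mean shows.** With k subjects each falling by d mm Hg among n, the mean shifts by k × d / n. Here n = 850 (Section 13.2), and d is assumed.

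- One fall of 50: 1 × 50 / 850 = 0.06 mm Hg
- Three falls of 50: 3 × 50 / 850 = 0.18 mm Hg
- Five falls of 50: 5 × 50 / 850 = 0.29 mm Hg

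If the table is split by regimen and enrolment is even (an assumption), n = 850 / 5 = 170:

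- Two falls of 40 to 60: 80 / 170 to 120 / 170 = 0.47 to 0.71 mm Hg
- Five falls of 40 to 60: 200 / 170 to 300 / 170 = 1.18 to 1.76 mm Hg

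**2. What the minimum shows.** Take one simulated regimen of 170 subjects, with background changes drawn with an assumed SD of 12 mm Hg and limited to ±33. Replacing 1 or 5 of them with large falls (45 to 60 mm Hg) gives:

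| Subjects with a large fall | Mean | SD | Median | Minimum |
|---|---|---|---|---|
| 1 | -1.3 | 11.6 | -0.4 | -60 |
| 5 | -2.4 | 13.4 | -1.0 | -60 |

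The minimum is the same for one subject and for five.

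**3. Why the minimum change does not identify who passed the cut-off.** A 30% fall is 0.3 × 110 = 33 mm Hg from a baseline of 110, and 0.3 × 160 = 48 mm Hg from 160. The limit of 90 is reached by a fall of 110 − 90 = 20 from 110, but only by 160 − 90 = 70 from 160. A change of -35 mm Hg therefore passes the cut-off from 110 (to 75) and does not from 160 (to 125, a 22% fall). The count needs each subject's own baseline.

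**4. The pre-dose window.**

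- Groups 4 and 5: study drug follows lidocaine by 3 minutes, so 5 − 3 = 2 minutes of the window lie before the lidocaine injection ends. The time to inject 15 mL is not given. If it is 0.5, 1 or 2 minutes (assumed), then 1.5, 1 or 0 minutes remain before the needle goes in. A standing reading would in practice come before lidocaine.
- Groups 1, 2 and 3: 30, 10 and 5 minutes of cooling separate lidocaine from study drug (Section 9.3.2). A reading taken in the last 5 minutes follows lidocaine.

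**5. Posture, side by side.** At 5 minutes, Section 11.2.1 wants standing and sitting, while Table 2-1 and Sections 10.1.2 and 10.1.4 want sitting only. These passages agree on sitting only at 15 and 30 minutes. All include a sitting pre-dose reading and a sitting reading at 5 minutes.

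**The case against.** A reader might infer that hypotension would go uncounted altogether. The documents do not support that. Section 11.2.2 treats clinically relevant observations at a visit as AEs. Section 11.2.1 requires anaphylactic and anaphylactoid events to be recorded with times. Section 13.4.4.1 tabulates AEs as numbers and percentages for each injection procedure, with listings. The planned minimum would also expose an extreme value. What remains is readings past the cut-off that nobody reports, for which the AE route depends on recognition by an open-label investigator.

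Nor is the cut-off on its own the anaphylaxis definition. It stands under the third criterion, which applies after exposure to an allergen already known for that patient, and exclusion criterion 14 keeps out subjects with a history of allergic reaction to capsaicin or the named excipients. The count would be a general hypotension screen. This objection stands and determines how the table should be labelled.

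Four further readings are tempting and go too far:

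- *The posture and window conflicts cause the missing count.* They do not. A count can be tabulated whatever their resolution.
- *Mixed postures spoil the 5-minute comparison.* A sitting reading is due at 5 minutes under either text, so sitting can be compared with sitting.
- *Groups 4 and 5 cannot meet the pre-dose window.* This is unproven. The window is approximate, the injection time is not given, a seated reading with the needle in place is not ruled out, and the 5 minutes of seated rest can begin during the 45-minute pre-cooling.
- *Changes from Baseline are not comparable between regimens.* That holds only if Baseline means the pre-dose reading. Section 13.4.4.3 does not say, and Section 13.4.4.4 speaks of Baseline at Screening for the ECG.

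Finally, Section 13.4 calls itself a summary and promises a detailed SAP before database lock. That SAP could add the count, but the text available here does not commit to it.

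**Conclusion.** The point holds in a limited form and is worth acting on. The planned vital-sign tables would not systematically count, by regimen, the subjects whose post-injection systolic pressure passes the protocol's own cut-off without an AE report. Three falls of 50 mm Hg among 850 subjects shift the mean by 0.18 mm Hg, and the minimum does not give the number. The size of the falls, the even split into 170 per regimen and the background SD are assumptions; the absence of a count in Section 13.4.4.3 is not.

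Separately, and independently of the count, the passages on posture at 5 minutes contradict each other. The pre-dose window is tight against the 3-minute single-needle sequence, so the pre-dose reading may precede lidocaine in Groups 4 and 5 and follow it in Groups 1 to 3.

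**What to change.** **Analysis (Section 13.4.4.3 or the SAP, before database lock).**

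- Define the vital-sign baseline as the sitting pre-dose reading.
- By regimen, injection (first or second) and time point (5, 15 and 30 minutes), give the number and percentage of subjects with systolic pressure below 90 mm Hg or a fall of more than 30% from that baseline, comparing sitting with sitting only.
- Add a subject listing, cross-referenced to AEs, with the pre-dose value shown.
- Label both as a hypotension screen, not as a diagnosis of anaphylaxis.

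**Reconciliation by the sponsor.** Bring Section 11.2.1, the vital-signs footnote to Table 2-1, and Sections 10.1.2, 10.1.4 and 10.3.3.2.1 into agreement on posture. Reconcile the pre-dose window with the single-needle sequence in Section 9.3.2 and the Synopsis, stating where the pre-dose reading falls relative to lidocaine in each group. No view is taken here on which rule is right.

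**Cost.** One table and one listing from data already due to be collected. The wording changes need a protocol amendment under Section 14.8.
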